A9. ClinicalTrials.gov Registration

Does this protocol/trial require registration on ClinicalTrials.gov due to it: meeting the definition of an Applicable Clinical Trial, being required under the terms and conditions of an award, or being proposed to be published in ICMJE journals? Yes

Who will be responsible for registering and maintaining the registration of this Applicable Clinical Trial? The BCM PI will register the trial because either:

- the trial is BCM PI-initiated,
- BCM is the lead site of this multicenter trial, or,
- the industry sponsor has instructed the BCM PI to register the trial, or,
- registration of this trail is required as a term and condition of the reward by the funding agency.

ClinicalTrials.gov Identifier: NCT04307355

Section B: Exempt Request

B. Exempt From IRB Review

Not Applicable

Section C: Background Information

Reduction mammoplasty is a procedure in which a volumetric reduction of the breast is done for cosmetic purposes. This technique includes an infra-mammary perpendicular incision joined by a T-inframammary fold in it; central area, that further continue vertically until surrounding the nipple perimeter.

The likelihood of poor healing outcomes and adverse events (e.g., wound dehiscence, thick scar, itchy or unsortable scars) at the T-inframammary fold (anchor incision) of the breast wound incision is relatively high (estimated to be 10%-15%). This pure outcome is attributed to the corner (as a result of the T-inframammary fold) low blood supply. Given the fact that there are two corners in this particular procedure, the chances of adverse events are higher due to the point of most tension for the entire breast. Continuous oxygen therapy may reduce the likelihood of poor outcomes and adverse events.

In our institution, the Plastic Surgery Department utilizes Dermabond glue (sano acrylic) and Prineotape (air and water sealed) to close the wound around the areola and over the T-inframammary fold. Depending on the incision size, a JP drain could be placed (10% of the cases). Furthermore, the Prineo tape is kept on for a period of 3 weeks. Once it is removed, the incisions are normally healed. However, if wound dehiscence presents, it normally happens between the second and third post-operative week. Then, the Prineo tape has to be removed before the expected time period. Therefore, an external dressing might be able to avoid wound dehiscence during this period.

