Section D: Purpose and Objectives

This is an exploratory randomized controlled trial study to test feasibility, acceptability, and proof of concept efficacy of Continuous Diffusion of Oxygen (CDO) adjunct therapy for decreasing healing time and reducing tissue dehiscence post breast reconstruction. We will assess the benefit of this novel adjunct therapy on successful closure, tissue oxygenation, scar appearance, and patients centered outcomes including perception of benefit, pain, sleep quality, and quality of life. Since all procedures are bilateral, an internal randomization will be performed based on breast side (left or right). The patients will be given CDO in one breast defined as intervention breast. A 5x5 cm CDO dressing will be placed by the plastic surgeon over the T-inframammary fold after the Dermabond glue and Prineo tape are placed. Then, Silagen (a silicon sheet) will be placed on top of the CDO dressing to secure it in place. The remaining parts of the incision will be covered with Dermabond Glue and Prineo tape. On the contrary, the control breast will be given the standard dressing (Dermabond + Prineo tape). The study device OxyGeni is a Class II medical device which has US Food and Drug Administration (FDA) 510(k) clearance, CE-Mark approval and a Health Canada license for the treatment of wounds.

Outcomes will be assessed on weekly-basis up to 4 weeks. Here are the aims and hypotheses for this study:

Aim1: To assess effectiveness of CDO adjunct therapy in reducing the likelihood of wound complication post-surgical

closure.

H1: CDO adjunct therapy will reduce the likelihood of surgical wound complication including dehiscence and its volume, infection or surgical revision, compare to standard of care dressing.

Aim2: To assess changes in skin perfusion in patients treated with CDO adjunct therapy.

H2: CDO adjunct therapy will improve tissue oxygen saturation in >50% of the patients as compared to baseline (measurements at baseline, 2 weeks, and 4 weeks).

Aim3: To evaluate changes in quality of life, anxiety during dressing change, and psychosocial parameters in patients with a surgical wound treated by CDO adjunct therapy

H3: CDO adjunct therapy will improve subject quality of life, reduce anxiety, and reduce perceived pain and physiological stress response during dressing change compared to the control group.

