Please note that subjects will be consented before performing any study related measurements. This study will not bring any direct costs to the subject. The subject's medical insurance will be billed for all standard of care procedures.

Eligible subjects will be internally randomized and will receive the intervention for 4 weeks. Each subjects will receive standard of care for wound treatment. Intervention side will receive adjunct Continuous Diffusion of Oxygen (CDO) therapy using a novel dressing, which facilitates continuous supply of oxygen to the wound inside the wound dressing using a portable device named OxyGeni . We will collect patient demographics (e.g., age, sex, height, weight, race, ethnicity, marital status, level of education, etc), relevant medical history (e.g., comorbidity, type of surgery, number of prescription and over counter medication, etc), and relevant social factors (e.g., marital status, years of education, type of work, tobacco history, etc) at baseline. Primary outcomes include tissue oxygenation (assessed using Kent Imaging system) and incidence of wound complications (e.g. dehiscence, infection, and surgical revision). Primary outcomes will be assessed at baseline and on a weekly basis for up to 4 weeks. Secondary and exploratory outcomes include inflammation (assessed using a KENT camera), pain (assessed visual analog scale). The secondary and exploratory outcomes will be assessed at baseline and week-4. Other optional assessments include quality of life (NIH Global Health PROMIS), depression (Center for Epidemiologic Studies Depression Scale, CES-D), cognitive function MoCA), and psychosocial metrics (e.g. fatigue, anxiety, frailty, sleep, etc). These assessments are optional and will be done upon time availability and patient acceptance. We anticipate that duration of all assessments will not exceed 60 minutes. We will be reviewing the billing records for our

patients to explore costs of both groups. We may visit the patient's home for an appointment that doesn't require the physician present or to fix any issues with the device.

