Wound Assessment (primary outcome): A digital photo/video of wound will be taken for wound size verification, estimation of wound size, success of wound healing, and determination of wound dehiscence. Measurement will be performed at every visit.

Pain Intensity Assessment (VAS) (secondary outcome): The subject will be provided with a numeric pain scale where he/she will report pain intensity. Research staff will document subject's pain level. (Collected at every visit)

Adverse Event Reporting: Research Staff will document and report any study/non study related incident as per institution regulations. (Collected at baseline and visits 1-4)

Device Acceptability Questionnaire: To determine patient perception of benefit, perceived ease of use, and attitude toward the use of device, we will use a technology acceptance model (TAM) questionnaire tailored for the purpose of this study. This assessment will be done at the conclusion of the study (week-4)

Questionnaires (optional): Quality of Life (PROMIS), functional status, Frailty Status (TSFI), Cognitive Assessment, and Sleep Quality (PSQI). To evaluate functional status, we will use well accepted and validated general functional assessment instruments. PFIBS for Pain Frequency, Intensity and Burden Scale, MOCA for Mental Exam, and Visual analog scale for pain. (All questionnaires are optional and may be done at any study visit upon time availability and patient acceptability). We will add the already approved questionnaires for the parent study, which include pain. Additionally, we will include Likert Scales (Moon SH et al, 2011; Singer AJ et al 1997; Hollander JE et al 1995; and Ridway DM et al 2007) and Patient Attitude to Scarring Scale (PASS, Kantor J et al 2016) and Patient and Observer Scar Assessment Scale (POSAS) to assess the following patient-reported outcomes: patient satisfaction and cosmetic appearance to evaluate scar itchy, perception of scar thickness, scar discomfort, and pain for each wound side (i.e., left and right breast). SCAR may be used to assess plastic surgeon satisfaction with the scarring. These questionnaires will be answered to the best of the participant's abilities. Should the participant lack certain capacities that make it difficult for them to respond to these questionnaires, they will not be conducted with that participant.

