The primary outcomes of this study are 1) tissue oxygen saturation level measured using Kent Imaging system and 2) incident of wound related adverse events (e.g., incident wound dehiscence, infection, scar size, and surgical revision). Secondarily outcomes include pain, wound outcomes (e.g. wound size, scar size, wound healing rate, etc assessed using digital photography), area of inflammation (assessed using KENT), and pain (assessed using VAS). Exploratory outcomes include patient quality of life, sleep quality, anxiety, and depression. Baseline between group comparison will be dine using two-sample t-tests, Mann-Whitney U-test, or Chi-square depend on scale/distribution of the variables (i.e., parametric, non-parametric, or binary). We will use general mixed linear model and post-hoc analysis to examine difference between

groups (time, group, and time X group effect) for skin perfusion. We will adjust the results based on baseline incision wound size and duration between baseline and last visit assessment. Subjects with at least one week continue treatment will be included in the analysis. Controlled variables include age, BMI, baseline vascular health. We will use chi-square to estimate whether the number of wound complication incidents is less in the intervention group compared to the control group. Chi-square or repeated ANOVA or Mann-U test depend on scale/distribution of the variable will be used for secondary and exploratory outcomes.

Section H: Potential Risks/Discomforts

H1. Potential Risks/Discomforts

Describe and assess any potential risks/discomforts; (physical, psychological, social, legal, or other) and assess the likelihood and seriousness of such risks:

As any new investigational device, there are some risks, which are anticipated to be minimal in this study. Some of potential risks could be: * Skin related discomfort, erythema (redness), skin rash, dryness and itching. * Skin allergic reaction to dressing adhesive. * Tenderness/minor ache around the dressing application area * Heat sensation and/or perspiration with wearing dressing * Some impairment of mobility due to dressing unit

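### Wound size has no fixed role or paired analysis: F2 labels it primary, G2 secondary with an independent-groups test, and no value is set for a breast that stays closed or is revised

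*Combined protocol and SAP*

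**What the plan says.** The wound outcome is described in four places.

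- **Section D, H1:** "CDO adjunct therapy will reduce the likelihood of surgical wound complication including dehiscence and its volume, infection or surgical revision" compared with standard dressing. The hypothesis is about likelihood, yet it contains a volume. H1 does not use the word primary.
- **F2, outcome paragraph:** the wound primary is "incidence of wound complications (e.g. dehiscence, infection, and surgical revision"). Size is not mentioned.
- **F2, Wound Assessment item:** "Wound Assessment (primary outcome): A digital photo/video of wound will be taken for wound size verification, estimation of wound size, success of wound healing", and the sentence goes on to include determining whether dehiscence has occurred. It adds: "Measurement will be performed at every visit".
- **G2:** the second primary outcome is "incident of wound related adverse events (e.g., incident wound dehiscence, infection, scar size, and surgical revision"). The next sentence reads "Secondarily outcomes include pain, wound outcomes (e.g. wound size, scar size, wound healing rate, etc assessed using digital photography"). Scar size is therefore in both lists, and dehiscence volume is in neither.

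For analysis, G2 applies a chi-square to the number of complication incidents. For secondary and exploratory outcomes it offers chi-square, repeated ANOVA or the Mann-Whitney test, depending on the variable's scale and distribution. Section D and F1 say that side (left or right) is randomised within each patient. F1 ends the weekly assessments at 4 weeks, full healing or surgical revision, whichever is first.

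**The concern.** There are three gaps.

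1. **Role.** With wound size under a primary label in one place and secondary in another, a size or healing result could be presented as either once the data are known. The same holds for scar size within G2.
2. **Method.** Volume is hypothesised but has no analysis. Wound size, if skewed, goes to a test for two independent groups although each patient supplies one breast to each side.
3. **Scoring.** Every incision is surgically closed, so a breast that stays closed has no dehiscence to measure. A revised breast may have no later assessment. The plan gives a value for neither. An analyst could therefore compare sizes among opened breasts only, which selects on an event that CDO is hypothesised to change. The groups so formed are no longer those created by randomisation.

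**Working it through.** **Plan's own figure.** G1 gives 30 patients, justified by resources and feasibility, with no alpha, power, effect or SD. There is nothing to reproduce. Thirty patients give 30 CDO and 30 control breasts.

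**Assumptions not in the documents.** The 10%-15% in Section C is read as a per-breast opening rate. It is an upper reading, because the figure covers all poor healing outcomes, including thick or itchy scars, and has no stated unit. CDO is assumed to halve the rate. Breasts are treated as independent except in the simulation.

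**How many breasts would have a size**

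- Control: 30 × 0.10 = 3.0 to 30 × 0.15 = 4.5.
- CDO: 30 × 0.05 = 1.5 to 30 × 0.075 = 2.25.
- Chance of no opened CDO breast: 0.95^30 = 21%; 0.925^30 = 10%.
- Patients with both breasts opened: 30 × 0.10 × 0.05 = 0.15; 30 × 0.15 × 0.075 = 0.34. A paired comparison restricted to opened breasts is not feasible.

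**What an opened-only Mann-Whitney test could show.** With a and b opened breasts, the smallest two-sided exact p is 2/C(a+b, a).

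| Opened breasts | Smallest p |
|---|---|
| 3 vs 2 | 2/10 = 0.20 |
| 4 vs 2 | 2/15 = 0.13 |
| 5 vs 2 | 2/21 = 0.095 |

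Summing binomial probabilities over the counts for which p ≤ 0.05 is attainable gives 4.9% (10% vs 5%) and 25.6% (15% vs 7.5%). At an assumed 5% vs 2.5% it is 0.1%.

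**Direction of an opened-only comparison.** Suppose CDO prevents exactly the smaller half of openings.

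- Exponential sizes: mean above the median ÷ overall mean = 1 + ln 2 = 1.69. Total volume = 0.5 × 1.69 = 0.85 of control, a 15% fall.
- Lognormal sizes, log-SD 0.5: ratio = 2Φ(0.5) = 1.38. Total = Φ(0.5) = 0.69, a 31% fall.

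CDO then looks worse on mean size while total volume falls.

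A simulation (40,000 trials of 30 pairs, latent within-patient correlation 0.5, lognormal sizes with median 1 and log-SD 0.8) compared the two scorings. Ranges run over opening rates of 10% and 15%.

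| What CDO prevents | Opened-only means, control vs CDO | CDO mean larger, opened only* | CDO mean larger, closed = 0 |
|---|---|---|---|
| Smaller half | about 1.4 vs 2.2 | 78%-80% | 38%-39% |
| Smaller half, rest shrunk 20% | about 1.4 vs 1.7 | 65%-66% | 30%-32% |
| Half at random | 1.38 vs 1.37-1.38 | 46% | 22%-26% |

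*Among trials with an opened breast on both sides.

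In the last row nothing reverses, but opened-only means hide the halving. With closed = 0, the all-breast means at 10% are 0.138 vs 0.069. In the first row they are 0.137 vs 0.108, so the true direction is restored.

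**What the paired test can do.** With m non-zero differences, the smallest two-sided p for a sign or signed-rank test is 2/2^m: 0.0625 for m = 5 and 0.031 for m = 6. The chance that a pair is non-zero is 1 − 0.90 × 0.95 = 0.145, or 1 − 0.85 × 0.925 = 0.214. The expected number of such pairs is 4.4 or 6.4, and the chance of at least 6 is 26% or 64%.

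**The case against.** A reader might infer that the plan compares sizes among failures. It does not say so. G2 includes subjects with at least one week of treatment and sets no restriction to dehisced breasts. Wound assessment takes place at every visit, and G2 foresees a baseline incision wound size, so a size for every breast fits the text at least as well. This stands: the gap is the missing value for a closed or revised breast. Incision size is still not extent of dehiscence, and the plan does not separate them.

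A reader might also infer that H1 makes volume primary and G2 demotes it. H1 has no such label, and G2 omits volume. The outcome paragraph of F2 and G2 agree on incidence, apart from scar size. The conflict on wound size rests on the Wound Assessment label, which may describe only what the photograph is for. The label nevertheless covers size and healing as written.

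Nor do the documents support saying that 10%-15% of breasts open, or that CDO would look harmful. The rate is a composite, and reversal requires CDO to prevent mainly smaller openings. The small counts also make a significant false harm unlikely.

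On pairing, G2 also offers repeated ANOVA. It does not say that breast is the repeated factor, and for a skewed outcome the test it names is Mann-Whitney. The pilot status lowers the stakes but does not remove the conflict between named primary and secondary outcomes.

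**Conclusion.** The point holds in limited form. The inconsistent role of wound size, the double listing of scar size, the unanalysed volume and the independent-groups test for within-patient data are all visible in the text and need no assumption. The opened-only comparison is permitted by silence, not planned. Its possible harm ranges from hiding a benefit (prevention unrelated to size) to reversing its direction in 78%-80% of evaluable simulated trials (smaller half prevented). Those figures depend on the assumed size distribution, correlation and halving. The counts of 3-4.5 and 1.5-2.25 opened breasts are illustrative upper figures, since the documents give no dehiscence rate. The sponsor should correct this before analysis. It does not affect the trial's feasibility aims.

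**What to change.** - **Primary:** state the wound primary as incidence of complications per breast, including dehiscence yes/no, in H1, both F2 entries and G2. Remove the volume from H1 or name it there as secondary. Limit the primary label on Wound Assessment to the determination of dehiscence. List scar size once, as secondary.
- **Scoring:** define dehiscence size as a secondary outcome for every randomised breast: the largest size up to week 4, and zero if the breast stays closed. Prespecify a score for a revised breast, for example the largest size recorded before revision, with worst rank as a sensitivity analysis.
- **Analysis:** replace Mann-Whitney for this outcome by the within-patient difference, CDO minus control, over all pairs (Wilcoxon signed-rank or sign test). Describe sizes among opened breasts without a test.

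The cost is wording in Section D, F2 and G2. Photographs are already taken at every visit, so no new data are needed. The drawback is many zero differences: the test will rest on few pairs and will often be unable to reach p ≤ 0.05. The score for a revised breast is a choice to be justified, because revision already counts as a primary event.

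### H2 judges the primary oxygenation outcome against the patient's own baseline, with no control breast and no deciding visit, and G2's controlled model is not explicitly tied to it

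*Combined protocol and SAP*

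**What the plan says.** Section D gives the second aim as "Aim2: To assess changes in skin perfusion in patients treated with CDO adjunct therapy". Its hypothesis, H2, is that "CDO adjunct therapy will improve tissue oxygen saturation in >50% of the patients as compared to baseline", with "measurements at baseline, 2 weeks, and 4 weeks". The hypotheses on either side of it do name a comparator: H1 ends with "infection or surgical revision, compare to standard of care dressing" and H3 with "physiological stress response during dressing change compared to the control group".

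Section G2 lists tissue oxygen saturation as the first of two primary outcomes. It plans a mixed linear model to examine differences between "groups (time, group, and time X group effect) for skin perfusion", the same term that Aim 2 uses. It adjusts for "baseline incision wound size and duration between baseline and last visit assessment" and sets one inclusion rule: "Subjects with at least one week continue treatment will be included in the analysis".

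Three further points bear on this:

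- F2 (baseline visit) places the first oxygenation image in surgery, at closure of the incision.
- F2 (tissue oxygen saturation) schedules imaging at every study visit, whereas H2 lists only weeks 2 and 4.
- F1 lets weekly assessment stop before week 4, at full healing or surgical revision.

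**The concern.** The baseline reading comes from a freshly closed wound, and later readings come from a wound one to four weeks into recovery. Any change that both breasts share over that time is credited to CDO, or held against it, when the treated breast is compared only with its own baseline. The randomized control breast exists to remove that shared change, and H2 leaves it out. H2 could be declared met when the control breast improved just as much, or not met because both breasts fell after closure.

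Two gaps add to this. With two visits listed and no rule for combining them, the criterion can be read in at least four ways. A patient with one week of treatment enters the analysis but may have no week-2 or week-4 reading, and H2 does not say whether that patient counts in the denominator.

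At stake is whether a report of improved oxygenation can be attributed to CDO. G1 says that initial results may lead to a larger sample, so the answer may inform that decision.

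**Working it through.** **Inputs from the documents.** N = 30 patients (G1); threshold above 50% (H2), so the smallest qualifying count is 16 of 30; visits at weeks 2 and 4 (H2). There is no plan figure to reproduce: G1 justifies N = 30 by budget and feasibility, and gives no alpha, power, effect size or SD.

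**Assumptions.** H2 is read as a simple count. The chance *p* that a breast reads above its baseline with no CDO effect is not documented, so it is varied. Patients are independent. The number evaluable is varied from 24 to 30.

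**1. One deciding visit, no CDO effect.** P(met) = Σ C(n,k) p^k (1−p)^(n−k), summed over k above n/2.

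| Assumed p | n = 30 (at least 16) | Range over n = 24 to 30 |
|---|---|---|
| 0.40 | 0.097 | 0.097–0.154 |
| 0.50 (pure noise) | 0.428 | 0.419–0.500 |
| 0.60 | 0.825 | 0.787–0.864 |
| 0.70 | 0.983 | 0.969–0.988 |

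A formal test of p > 0.5 would not cure this. At one-sided 5% it would need 20 of 30 (exact tail 0.049), and it would still not separate CDO from recovery common to both breasts.

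**2. Unstated visit rule, pure noise, n = 30.** The week-2 and week-4 changes share one baseline, so they are correlated (r). P(both up) = 1/4 + asin(r)/(2π), and P(either up) = 1 − P(both up) by symmetry. If the three readings are equally correlated, r = 0.5: P(both up) = 1/4 + 1/12 = 1/3 and P(either up) = 2/3.

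| r | H2 met if both visits must improve | H2 met if either suffices |
|---|---|---|
| 0.3 | 0.006 | 0.984 |
| 0.5 | 0.019 | 0.957 |
| 0.7 | 0.054 | 0.892 |

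**3. Unstated denominator, pure noise, one visit.**

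| Patients lacking the reading | Excluded | Counted as not improved |
|---|---|---|
| 6 of 30 | at least 13 of 24: 0.419 | at least 16 among 24 observed: 0.076 |
| 3 of 30 | at least 14 of 27: 0.500 | at least 16 among 27 observed: 0.221 |

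**4. A controlled count.** Count the patients whose change is larger in the CDO breast than in the control breast and apply a sign test, two-sided p = 2·P(X ≥ k | n, 0.5).

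| n | Smallest count with p < 0.05 | One fewer |
|---|---|---|
| 30 | 21 (p = 0.043) | 20 (p = 0.099) |
| 27 | 20 (p = 0.019) | 19 (p = 0.052) |
| 24 | 18 (p = 0.023) | 17 (p = 0.064) |

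If the CDO breast truly changes more in 70% of patients, this test succeeds with probability 0.589 at n = 30 and 0.389 at n = 24.

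**5. A controlled mean difference.** With no CDO effect, the baseline-adjusted paired difference was simulated 20,000 times per setting (n = 24 and 30; within-breast correlation 0.2 to 0.6; 40–70% of untreated breasts improving). It rejected in 4.8–5.3% of runs at week 4, 4.8–5.2% for weeks 2 and 4, and 4.8–5.3% for the mean of weeks 1–4. This follows from how the contrast is built and does not favour one choice of visits.

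**The case against.** The strongest reply is that H2 is a prediction in the objectives and not a decision rule. The analysis plan is G2, which contains no 50% criterion and does contain a model comparing the breasts. The term skin perfusion ties that model to Aim 2 and to no other aim. H4 and H5 also name no comparator, so the omission may be loose drafting. The rates, correlations and missing-reading counts used above are not in the documents, and no test of the 50% threshold is planned, so 43% is not the error rate of a planned test. A mixed model can use whatever readings exist, which weakens the denominator point. The study is labelled exploratory and a pilot.

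Much of this stands. A controlled oxygenation analysis is planned, and G2 does address unequal follow-up. The probabilities show how far the result depends on what is unstated; they do not estimate this trial's risk. The pilot label argues against a higher rating.

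It does not remove the point. H2 is the only success statement the plan gives for this primary outcome. G2 neither replaces it nor says that the model, and which term of it at which visit, is the evidence for an oxygenation effect. Both routes remain open, and they answer different questions.

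**Conclusion.** The concern holds and should be fixed. The defect is a mismatch between a before/after hypothesis and a controlled analysis, both left without a deciding visit; it is not the absence of a controlled analysis. That the wording omits the control breast and the deciding visit is certain from the text. The size depends on the reading of H2 as a count and on undocumented rates. Over the assumed range of 40–70% of untreated breasts improving, the chance of meeting H2 with no CDO effect runs from 10% to 98% with 30 evaluable patients. Under noise alone, the choice of visit rule or of denominator also shifts the answer substantially.

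**What to change.** 1. Restate H2: tissue oxygen saturation is higher in the CDO breast than in the same patient's control breast.
2. Name in G2 one deciding within-patient contrast at a prespecified visit or set of visits (for example week 4, weeks 2 and 4, or the mean over weeks 1–4). Account for pairing, adjust for baseline saturation, and state how a patient without the chosen reading is handled. Suggested sentence: *The deciding analysis for Aim 2 is the within-patient CDO-minus-control difference in tissue oxygen saturation at [chosen visit or visits], adjusted for the between-breast difference in baseline saturation.*
3. Report the before/after percentage descriptively, for both breasts.
4. If a responder count is kept, base it on which breast changed more, with the sign test and cut-offs shown in the working.
5. Confirm from Table 1, an attachment not available to this review, that both breasts are imaged at baseline and at every visit used.

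The cost is a reworded hypothesis, a short addition to G2 and that check. If control-breast images are already scheduled, no data collection is added. The price is a criterion that is harder to meet, as the sign-test success rates in the working show.
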